8.5.3 Graphical Presentation of Pharmacokinetic Data Statistics

All mean (arithmetic mean and/or gmean) plots or combined plots showing all subjects by treatment and treatment sequence are based on the PK analysis set. Individual plots by subject are based on the Safety analysis set.

For consistency, the plasma concentration values used in the mean (arithmetic mean and/or gmean) data graphs are those given in the descriptive statistics summary table for each time point.

For gmean concentration-time plots, NQ values are handled as described for the descriptive statistics; if the geometric mean is NQ, the value plotted is zero for linear plots and missing for

semi-logarithmic plots. Any gmean±gSD error bar values that are negative are truncated at zero on linear concentration-time plots and omitted from semi-logarithmic plots.

For individual plots, plasma concentrations which are NQ prior to the first quantifiable concentration are set to a value of zero (linear plots only). After the first quantifiable concentration, any NQ plasma concentrations are regarded as missing.

Data permitting, the following figures are presented as appropriate:

Figures for the mean (arithmetic mean and/or gmean) plasma concentration-time data (with ±Std Dev and/or ±gSD error bars) presented on both linear and semi-logarithmic scales using scheduled post-dose time as follows:

- AZD4041 in both the presence and absence of Morphine – Day 8 and 15
- Morphine in the absence and presence of AZD4041 – Day 1 and 15
- Morphine metabolites in the absence and presence of AZD4041 – Day 1 and 15

Individual subject plasma concentration-time data graphically presented on both linear and semi-logarithmic scales using actual time post-dose as:

- AZD4041 in the absence of Morphine - Day 8 and AZD4041 in the presence of Morphine – Day 15
- Morphine and its metabolites in the absence of AZD4041 – Day 1 and Morphine and its metabolites in the presence of AZD4041 – Day 15

Combined individual plasma concentration versus actual time after dose will be plotted on both the linear and semi-logarithmic scale, with the individual profiles for the same analyte in the different periods overlaid on the same plot as described below:

For treatment sequence 1:

- AZD4041 in the absence of Morphine - Day 8 and AZD4041 in the presence of Morphine – Day 15
- Morphine in the absence of AZD4041 – Day 1 and Morphine in the presence of AZD4041 – Day 15
- Morphine metabolites in the absence of AZD4041 – Day 1 and Morphine metabolites in the presence of AZD4041 – Day 15

For treatment sequence 2:

Morphine on Day 1 and 15.

Morphine metabolites on Day 1 and 15.

These plots will be based on the PK analysis set. Focus plots may be provided if there will be no clear distinction among profiles. Geometric mean (\pm gSD) plasma trough concentration (C_{trough}) of AZD4041 versus study day will be plotted on linear scale. Additional plots may be produced if deemed appropriate to summarise and present PK data.

Figures presenting the point estimate and associated two-sided 90% confidence intervals for the ratio of PK parameters (for AZD4041: AUC_T, C_{max,ss}, C_{trough,ss}; for morphine and metabolites: C_{max}, AUC_{0-t}, AUC_{0-∞}) for each comparison as mentioned above.

Figures for the arithmetic mean urine concentration-time data (with \pm Std Dev error bars) presented on both linear and semi-logarithmic scales using scheduled post-dose time as follows:

- Arithmetic mean of accumulated fraction (%) of AZD4041

8.5.4 Plasma Concentration Data

PK concentration data listings present to the same number of significant figures as the data received from the bioanalytical laboratory (usually but not always to 3 significant figures) and against the same units as received.

PK concentration descriptive statistics present 4 significant figures with the exception of the min and max which present 3 significant figures and n and n<LLOQ which present as integers.

8.5.5 Pharmacokinetic Parameter Data

PK parameter listings are presented according to the following rules:

- C_{max}, C_{trough}: present to the same number of significant figures as received from the bioanalytical laboratory
- T_{max} and t_{last}: present as received in the data, usually to 2 decimal places
- AUC_{inf}, AUC(0-t), AUC_T, AUC_{extr}, λ_Z, t^{1/2}/λ_Z, CL, CL_{ss/F}, V_{zss/F}, V_z, all ratios of PK, Rsq adj, Ae, fe and CLR: present to 3 significant figures
- n obs: present as an integer (no decimals)

The descriptive statistics for PK parameter data are presented to 4 significant figures with the exception of the min and max which are presented to 3 significant figures apart from the following:

- λ_Z: present to 5 significant figures with min and max to 3 significant figures
- t_{max} and t_{last}: present as received in the data, usually to 2 decimal places
- number of values (n): present as an integer

9 SAFETY ANALYSIS

9.1 Respiratory Depression Analysis

Summary statistics and inferential analysis for respiratory depression endpoints will be presented for all subjects who completed all EtCO₂ assessments in addition to the Safety Population, when possible. Incidence of increased EtCO₂ of at least >50 mmHg will be summarized by treatment and time point using frequency tables. Mean time to each increased EtCO₂ episode of at least >50 mmHg, mean duration of each increased EtCO₂ episode of at least >50 mmHg, and mean postdose EtCO₂ will be summarized by treatment and time point using descriptive statistics.

Maximum postdose increase in EtCO₂ E_{max} (postdose – predose) will be summarized by treatment using descriptive statistics and inferential analysis. EtCO₂ averages (predose average from Days 2 to 15), and postdose average on Day 15 will also be summarized by treatment using descriptive statistics and inferential analysis. For each event of significantly increased ETCO₂, type of medical intervention used will be listed.

Incidence of reduction in SpO₂ to <92% will be summarized by treatment and time point using frequency tables. Mean time to reduction in SpO₂ to <92%, mean duration of reduction in SpO₂ to <92%, and mean postdose SpO₂ will be summarized by treatment and time point using descriptive statistics. Maximum postdose reduction of SpO₂ E_{max} (predose – postdose) will be summarized by treatment using descriptive statistics and inferential analysis. SpO₂ averages (predose average from Days 2 to 15), and postdose average on Day 15 will also be summarized by treatment using descriptive statistics and inferential analysis. For each event of significantly reduced SpO₂, type of medical intervention used will be listed.

Incidence of reduced respiratory rate to <6 breaths/min will be summarized by treatment and time point using frequency tables. Mean time to each reduced respiratory rate episode of < 6 breaths/min, mean duration of each reduced respiratory rate episode of <6 breaths/min, and mean postdose respiratory rate will be summarized by treatment and time point using descriptive statistics. Maximum postdose decrease in respiratory rate E_{max} (predose – postdose) will be summarized by treatment using descriptive statistics and inferential analysis. Respiratory rate averages (predose average from Days 2 to 15), and postdose average on Day 15 will also be summarized by treatment using descriptive statistics and inferential analysis.

For EtCO₂, SpO₂, and respiratory rate the following figures will be generated:

- 1) Sequence 1: Mean (\pm SD) treatment by time point for Day 1 Morphine alone matched to Day 15 Morphine + AZD4041
- 2) Sequence 2: Mean (\pm SD) treatment by time point for Day 1 Morphine alone matched to Day 15 Morphine + Placebo
- 3) Mean (\pm SD) treatment by time point for Days 2-15 predose AZD4041 vs. Days 2-15 predose Placebo
- 4) Boxplot for E_{max} Day 1 Morphine alone matched to Day 15 Morphine + AZD4041
- 5) Boxplot for E_{max} Day 1 Morphine alone matched to Day 15 Morphine + Placebo
- 6) Boxplot for E_{max} Day 15 Morphine + AZD4041 vs. Day 15 Morphine + Placebo

For all inferential analysis on EtCO₂, SpO₂, and respiratory rate, mixed-effects models will be used for E_{max} and averaged measures. The models will include sequence, time (as a ordered factor variable), and the sequence-by-time interaction as fixed effects and baseline as a covariate, with 95% confidence intervals reported along with p-values. Homogeneity of treatment variances will be explored to determine if subject may be considered a random effect. The covariance structure for the mixed models will be heterogeneous compound symmetry. If the heterogeneous compound symmetry model does not converge, then a compound symmetry structure will be used and a footnote will be added to identify the results as using a different covariance structure than usual. The kenwood-roger adjustment for the degrees of freedom will be used when calculating p-values due to the small sample size.

The maximum postdose decrease in respiratory rate (E_{max (predose - postdose)}) is the primary criterion. In addition to the primary criterion, maximum postdose reduction in SpO₂ (E_{max (predose - postdose)}) and The maximum postdose increase in EtCO₂ (E_{max (postdose - predose)}) will have the following contrasts calculated in the mixed-effects models:

- 1) Morphine + AZD4041 (Day 15) vs Morphine alone (Day 1) [Sequence 1]
- 2) Morphine + Placebo (Day 15) vs Morphine alone (Day 1) [Sequence 2]
- 3) Morphine + AZD4041 (Day 15) vs Morphine + Placebo (Day 15) [Sequence 1 vs Sequence 2]

For EtCO₂, SpO₂, and respiratory rate averages (predose average from Days 2 to 15), and postdose average on Day 15, the following contrasts will be explored in the mixed-effects models:

- 1) (postdose): Morphine + AZD4041 (postdose average Day 15) vs (predose): AZD40401 (predose average Days 2-15)
- 2) (predose): Morphine + AZD4041 (predose average Days 2-15) vs (predose): Morphine + Placebo (predose average Days 2-15)

9.2 12-lead digital ECG Statistical Methodology

From the dECG data, the following parameters will be derived:

- 1) QTcF will be calculated as QTcF = QT*RR^{-1/3}, where the QT interval is in milliseconds and the RR interval is in seconds.
- 2) Heart rate will be calculated, based on the RR interval as HR = 60/RR interval, where the RR interval is in seconds.
- 3) Calculation of derived parameters will be performed after smoothing of QT and RR data.

The dECG data will be smoothed on an individual basis before performing the derivations above and prior to calculation of any changes from baseline or descriptive statistics. For each subject it will be done as follows: the mean value of all the measurements will be taken provided that at least 4 measurements are present and the time between the first and last is greater than 2.75 minutes or else, the smoothed value at the corresponding target time point will be set to missing.

Digital ECG results will be listed by treatment (Morphine and AZD4041 vs Morphine and placebo) for each subject and time point and will include all individual and smoothed values of PR, RR, QRS, QT interval, and the derived values of QTcF and HR. All smoothed and derived

parameters will have changes from baseline derived and presented within subject and treatment group.

Descriptive statistics will be presented by treatment arm and time point for smoothed values and changes from baseline of smoothed values of PR, RR, QRS, QT; derived values and changes from baseline for QTcF and HR will also be included. The baseline for the dECG measurements will be the (smoothed) predose assessment on Day 1.

Outliers with respect to PR, QRS, HR, RR and QTcF will also be tabulated for the following categories, described below.

For QTcF these values will be reported per time point:

- Absolute value > 450 ms and ≤ 480 ms
- Absolute value > 480 ms and ≤ 500 ms
- Absolute value > 500 ms
- Increase from baseline > 30 ms and ≤ 60 ms
- Increase from baseline > 60 ms

The maximum postdose values for PR interval will be summarized by treatment according to the following categories:

- ≤ 220 ms
- > 220 and ≤ 240 ms (all instances flagged in the listing*)
- > 240 ms (all instances flagged in the listing **)

The maximum postdose values for QRS duration will be summarized by treatment according to the following categories:

- ≤ 115 ms
- > 115 and ≤ 119 ms (all instances flagged in the listing*)
- > 119 ms (all instances flagged in the listing **)

The maximum/min postdose values for HR will be summarized by treatment according to the following categories:

- < 40 bpm (all instances flagged in the listing**)
- $40 - < 50$ bpm (all instances flagged in the listing*)
- ≥ 50 bpm and ≤ 100 bpm
- $> 100 - \leq 120$ bpm (all instances flagged in the listing*)
- > 120 bpm (all instances flagged in the listing**)

The maximum/min postdose values for RR will be summarized by treatment according to the following categories:

- < 500 ms (all instances flagged in the listing**)
- 500 ms - < 600 ms (all instances flagged in the listing*)
- ≥ 600 ms ≤ 1200 ms
- > 1200 ms ≤ 1500 ms (all instances flagged in the listing*)
- > 1500 ms (all instances flagged in the listing**)

All calculations of dECG parameters and reporting described in this section will be performed by AltaSciences who also will produce tables, box plots and graphs presenting the results. An Exposure Response (ER) analysis may be conducted that may include modelling of digital ECG variable data versus PK data of Morphine and/or morphine metabolites with and without AZD4041 co-administration and/or versus PK data of AZD4041 with and without morphine co-administration. This potential analysis will be described in a separate technical document and reported outside the final CSR for the study.

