## **STUDY SYNOPSIS**

Name of	AstraZeneca AB	
Sponsor/Company:		
Name of Product:	AZD4041	
Title of Study:	A Randomized, Double-blind, Placebo-controlled, Fixed Sequence Study to Assess the Effect on Respiratory Drive of Multiple Doses of AZD4041 When Co-administered With a Single Dose of Morphine in Healthy Recreational Opioid Users	
Study Development Phase:	Phase 1	
Objectives:	Primary objective:	
	• To assess the effect on respiratory drive of morphine administered after multiple doses of AZD4041 compared to morphine administered alone in healthy recreational opioid users	
	Secondary objectives:	
	• To assess the safety and tolerability of multiple doses of AZD4041 when co-administered with a single dose of morphine in healthy recreational opioid users	
	• To assess the pharmacokinetics (PK) of AZD4041 and morphine in healthy recreational opioid users	
	• To assess the impact of multiple dose administrations of AZD4041 on the PK of morphine and its metabolites	
	
 
To assess the impact of morphine on steady-state PK of AZD4041
 
To assess the renal clearance of AZD4041
 
	
Endpoints:	Safety:	
	Primary	
	Incidence of clinically significant changes in respiratory parameters, defined as:	
	
 
Incidence of increased end tidal carbon dioxide (EtCO2) of at least 10 mmHg compared to baseline or >50 mmHg (sustained for at least 30 seconds)
 
Incidence of reduction in SpO2 to <92% (sustained for at least
 
	
	30 seconds)	
	Secondary	
	• SpO 2 (%)	
	
 
Mean time to reduction in SpO2 to <92% (sustained for at least 30 seconds)
 
	
	
 
Mean duration of reduction in SpO2 to <92% (sustained for at least 30 seconds)
 
	

 
Maximum postdose reduction of SpO2 adjusted for baseline
 

 
Mean postdose SpO2
 

• EtCO 2 (mmHg)

 
Mean time to each increased EtCO2 episode of at least 10 mmHg compared to baseline or >50 mmHg (sustained for at least 30 seconds)
 

 
Mean duration of each increased EtCO2 episode of at least 10 mmHg compared to baseline or >50 mmHg (sustained for at least 30 seconds)
 

 
Maximum postdose increase in EtCO2 adjusted for baseline
 

 
Mean postdose EtCO2
 

• Respiratory rate (breaths/min)

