# 8.3.1. Safety Endpoints

The primary safety endpoints are:

- Incidence of increased EtCO2 of at least 10 mmHg compared to baseline or >50 mmHg (sustained for at least 30 seconds)
- Incidence of reduction in SpO2 to <92% (sustained for at least 30 seconds)

The secondary safety endpoints are:

- Mean time to reduction in SpO2 to <92% (sustained for at least 30 seconds)
- Mean duration of reduction in SpO2 to <92% (sustained for at least 30 seconds)
- Maximum postdose reduction of SpO2 adjusted for baseline
- Mean postdose SpO2
- Mean time to each increased EtCO2 episode of at least 10 mmHg compared to baseline or >50 mmHg (sustained for at least 30 seconds)
- Mean duration of each increased EtCO2 episode of at least 10 mmHg compared to baseline or >50 mmHg (sustained for at least 30 seconds)
- Maximum postdose increase in EtCO2 adjusted for baseline
- Mean postdose EtCO2
- Incidence of reduced respiratory rate to <6 breaths/min (sustained for at least 30 seconds)
- Mean time to each reduced respiratory rate episode of <6 breaths/min (sustained for at least 30 seconds)

- Mean duration of each reduced respiratory rate episode of <6 breaths/min (sustained for at least 30 seconds)
- Maximum postdose decrease in respiratory rate adjusted for baseline
- Mean postdose respiratory rate
- Incidence, frequency, severity and relationship of AEs
- Vital signs measurements (BP, HR, and oral temperature)
- ECGs (12-lead safety ECGs, 12-lead dECGs, and ECG telemetry)
- Clinical laboratory test results (clinical chemistry, hematology, coagulation, urinalysis)
- Physical examination findings
- Type of medical intervention used, summarized for each event of significantly increased EtCO2, reduced SpO2 or respiratory rate

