## 8.3.2. Safety Analysis

#### 8.3.2.1. Respiratory Depression Analysis

Summary statistics and inferential analysis for respiratory depression endpoints will be done using the Completer Population.

Incidence of increased EtCO2 of at least >50 mmHg will be summarized by treatment and time point using frequency tables. Mean time to each increased EtCO2 episode of at least >50 mmHg, mean duration of each increased EtCO2 episode of at least >50 mmHg, and mean postdose EtCO2 will be summarized by treatment and time point using descriptive statistics. Maximum postdose increase in EtCO2  $E_{max}$  (postdose – predose) will be summarized by treatment using descriptive statistics and inferential analysis. EtCO2 averages (predose average from Days 2 to 15), and postdose average on Day 15 will also be summarized by treatment using descriptive statistics and inferential analysis. For each event of significantly increased ETCO2, type of medical intervention used will be listed.

Incidence of reduction in SpO2 to <92% will be summarized by treatment and time point using frequency tables. Mean time to reduction in SpO2 to <92%, mean duration of reduction in SpO2 to <92%, and mean postdose SpO2 will be summarized by treatment and time point using descriptive statistics. Maximum postdose reduction of SpO2  $E_{max}$  (predose – postdose) will be summarized by treatment using descriptive statistics and inferential analysis. SpO2 averages (predose average from Days 2 to 15), and postdose average on Day 15 will also be summarized by treatment using descriptive statistics and inferential analysis. For each event of significantly reduced SpO2, type of medical intervention used will be listed.

Incidence of reduced respiratory rate to <6 breaths/min will be summarized by treatment and time point using frequency tables. Mean time to each reduced respiratory rate episode of < 6 breaths/min, mean duration of each reduced respiratory rate episode of <6 breaths/min, and mean postdose respiratory rate will be summarized by treatment and time point using descriptive statistics. Maximum postdose decrease in respiratory rate  $E_{max}$  (predose – postdose) will be summarized by treatment using descriptive statistics and inferential analysis. Respiratory rate averages

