2 STUDY OBJECTIVES

The objectives of the study and corresponding study endpoints are detailed in [Table 2-1](#).

Table 2-1 Objectives and Related Endpoints

Objective	Endpoint
Primary	
To assess the effect on respiratory drive of morphine administered after multiple doses of AZD4041 compared to morphine administered alone in healthy recreational opioid users	
 • EtCO₂ (mmHg): Incidence of increased EtCO₂ of at least 10 mmHg compared to baseline or >50 mmHg (sustained for at least 30 seconds) • SpO₂ (%): Incidence of reduction in SpO₂ to <92% (sustained for at least 30 seconds)
Secondary	
 • SpO₂ (%) ▪ Mean time to reduction in SpO₂ to <92% (sustained for at least 30 seconds) ▪ Mean duration of reduction in SpO₂ to <92% (sustained for at least 30 seconds) ▪ Maximum postdose reduction of SpO₂ adjusted for baseline ▪ Mean postdose SpO₂ • EtCO₂ (mmHg) ▪ Mean time to each increased EtCO₂ episode of at least 10 mmHg compared to baseline or >50 mmHg (sustained for at least 30 seconds) ▪ Mean duration of each increased EtCO₂ episode of at least 10 mmHg compared to baseline or >50 mmHg (sustained for at least 30 seconds) ▪ Maximum postdose increase in EtCO₂ adjusted for baseline ▪ Mean postdose EtCO₂

	
 • Respiratory rate (breaths/min) ▪ Incidence of reduced respiratory rate to <6 breaths/min (sustained for at least 30 seconds) ▪ Mean time to each reduced respiratory rate episode of <6 breaths/min (sustained for at least 30 seconds) ▪ Mean duration of each reduced respiratory rate episode of <6 breaths/min (sustained for at least 30 seconds) ▪ Maximum postdose decrease in respiratory rate adjusted for baseline ▪ Mean postdose respiratory rate • Incidence, frequency, severity, and relationship of AEs • Vital signs (blood pressure, heart rate, and oral temperature) • ECGs (12-lead safety ECGs, 12-lead digital ECGs, and ECG telemetry) • Clinical laboratory test results (clinical chemistry, hematology, coagulation, urinalysis) • Neurological examination findings • Columbia Suicide Severity Rating Scale (C-SSRS) findings • Physical examination findings • Type of medical intervention used, summarized for each event of significantly increased EtCO₂, reduced SpO₂, or reduced respiratory rate

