12 GENERAL INFORMATION RELATED TO DATA PRESENTATIONS

The formats and layouts of TFLs are provided in a separate document as common displays. Their numbering and general content follow the International Conference on Harmonisation (ICH) E3 guidelines. Actual formats and layouts may be altered slightly from those presented as necessary to accommodate actual data or statistics.

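### The planned EtCO2 event summaries count only values above 50 mmHg and leave out the 10 mmHg rise from baseline that is part of the primary endpoint

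*SAP*

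**What the plan says.** The endpoint is defined the same way throughout. SAP Section 2 (Table 2-1) gives the primary EtCO2 endpoint as "Incidence of increased EtCO₂ of at least 10 mmHg compared to baseline or >50 mmHg (sustained for at least 30 seconds"). Protocol 8.3.1 has the same two criteria and the same duration rule, "of at least 10 mmHg compared to baseline or >50 mmHg (sustained for at least 30 seconds"), as do the Synopsis and the objectives table in Protocol Section 2. The secondary endpoints for time to episode and episode duration use this definition too.

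The analysis text differs. SAP 9.1 states: "Incidence of increased EtCO₂ of at least >50 mmHg will be summarized by treatment and time point using frequency tables". It continues with "Mean time to each increased EtCO₂ episode of at least >50 mmHg, mean duration of each increased EtCO₂ episode of at least >50 mmHg". Protocol 8.3.2.1 likewise has an incidence "of at least >50 mmHg will be summarized by treatment and time point using frequency tables", and it uses the same threshold for time and duration. The phrase "of at least 10 mmHg compared to baseline or" appears in the definitions but nowhere in either analysis section.

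Neither analysis section repeats the 30-second condition. That omission is general. For oxygen saturation the SAP says only "Incidence of reduction in SpO₂ to <92% will be summarized by treatment and time point using frequency tables", and respiratory rate is treated the same way.

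**The concern.** The frequency table is the only analysis described for the incidence of this primary endpoint. Read literally, it counts a different and narrower event. A subject whose EtCO2 rises by 10 mmHg or more for long enough, but stays at or below 50 mmHg, meets the definition and is not counted. Their episode is also left out of the time and duration summaries.

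This study's primary objective is the effect on respiratory drive, so under-counting respiratory events is the undesirable direction of error. The SAP also carries two event definitions for one primary endpoint. SAP 5.1 treats as a priori what is defined before lock or unblinding. If the conflict is left open, someone must choose between the definitions later, possibly with the data in view.

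**Working it through.** There is no stated power, error rate or calculated sample size to reproduce: Protocol 8.5 and SAP 3.5 say that no formal calculation was made. The check is a comparison of texts followed by threshold arithmetic.

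**Does any other described output report the defined event?**

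- The mixed models in SAP 9.1 analyse maximum change and averages. These are continuous measures and do not count sustained episodes.
- SAP 9.1 lists the intervention used for each significantly increased EtCO2 event. This is a listing of interventions, and 9.1 does not define the qualifying event.
- The capnography alarms in Protocol 6.1.14 use both criteria, at whichever gives the lower value. An alarm becomes an adverse event only after a judgement of clinical significance, so adverse event tables do not count the endpoint.

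**Inputs (Protocol 6.1.9).** Site historical baseline EtCO2: mean 36.6 mmHg, SD 2.2 (8 subjects), and mean 36.1 mmHg, SD 3.88 (15 subjects). Expected baseline range: 34 to 48 mmHg.

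**Formulas.** For baseline *b*:

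- threshold of the defined event = the lower of *b* + 10 and 50;
- rise needed to be counted by SAP 9.1 = more than 50 − *b*;
- uncounted window = 50 − defined threshold.

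| Baseline (mmHg) | Defined threshold | Rise needed in SAP 9.1 | Uncounted window |
|---|---|---|---|
| 34 | 44 | more than 16 | 6 |
| 36.1 | 46.1 | more than 13.9 | 3.9 |
| 36.6 | 46.6 | more than 13.4 | 3.4 |
| 40 | 50 | more than 10 | 0 |
| 48 | 50 (*b* + 10 = 58, so the absolute criterion is lower) | more than 2 | 0 |

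The window closes at a baseline of 40 and there is no gap above it. Every value above 50 mmHg also meets the full definition, so under the same duration rule the count in SAP 9.1 can never exceed the defined count.

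**How many subjects would have a baseline below 40?** Assuming normal baselines with the historical means and SDs:

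- (40 − 36.6)/2.2 = 1.545, giving 93.9%;
- (40 − 36.1)/3.88 = 1.005, giving 84.3%.

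On that assumption the omitted criterion is the easier one to meet for roughly 84% to 94% of subjects.

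**What share of events would be missed?** The documents cannot answer this. As an illustration only, 400,000 draws per scenario were simulated with the two historical baselines and an assumed, independent, normal peak rise (mean 6 to 14 mmHg, SD 3 or 5). The count above 50 mmHg then missed between 31% and 76% of subjects meeting the full definition. The assumed rises are not from the documents and the result depends on them.

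**The case against.** The strongest reply is that this is a truncated sentence and not a decision about the analysis. A phrase joining at least with a greater-than sign is ungrammatical, and it is what remains if the words about the 10 mmHg rise fall out of the full definition. Table 2-1 states the endpoint correctly. If it may be read as supplying the missing 30-second rule, it could supply the missing criterion too. SAP 12 says: "The formats and layouts of TFLs are provided in a separate document as common displays". Those shells may use the full wording, in which case the reported result would be right.

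Much of this stands. A drafting slip is the likeliest cause, and the shells could not be checked. But the two omissions are not alike. Silence on duration can be filled from Table 2-1, whereas naming a single threshold contradicts it. Oxygen saturation and respiratory rate keep their full thresholds in the same section. Only EtCO2 loses a criterion, in all three summaries and in both documents. A programmer following SAP 9.1 would code values above 50 mmHg.

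A second reply is that other outputs cover the gap. The Synopsis describes clinically significant respiratory changes with both EtCO2 criteria, so the intervention listing may include 10 mmHg rises, and some alarms will appear as adverse events. That is fair, but neither gives the incidence of the defined event.

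A third reply is that the harm is limited. No hypothesis test is specified for this incidence, the models of maximum change and averages are unaffected, and the same threshold would apply on both morphine days and in both sequences. This also stands: no bias between treatments has been shown. What is lost is sensitivity, and agreement between the endpoint and its analysis.

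Finally, the historical cohorts are small and were healthy volunteers, not this trial's population, so the arithmetic shows where the gap lies and not how many events fall in it. That is correct.

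**Conclusion.** The concern holds. As written, SAP 9.1 and Protocol 8.3.2.1 do not analyse the primary EtCO2 endpoint, or its time and duration companions, as both documents define them. The text is wrong as it stands, which is more than a missing detail, and it needs correcting before lock.

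The direction is certain given a common duration rule: the planned count is at most the defined count, and it can fall short only for subjects with a baseline below 40 mmHg. At the historical means the gap is 3.4 to 3.9 mmHg wide, and it reaches 6 mmHg at the bottom of the expected range. The 84% to 94% figure rests on normality and on two small cohorts. The number of events lost is unknown. The conclusion is confined to the text of the protocol and SAP.

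**What to change.** Before database lock and unblinding:

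- In SAP 9.1, replace the threshold above 50 mmHg with the full Table 2-1 definition, including the 30-second condition, in all three places: incidence, time to episode and duration.
- Check the table shells against that wording.
- Align Protocol 8.3.2.1 at the next amendment. Until then, a sentence in SAP 9.1 saying that it follows the endpoint in Protocol 8.3.1 would explain the remaining difference.
- A row for values above 50 mmHg alone may be kept as supportive, if the recorded data allow it.

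The cost is wording and minor programming. No stand-alone amendment is needed, because Protocol 8.3 leaves the safety statistics to the SAP and Protocol 8.3.1 already states the full endpoint. The main change needs no new assessment: Protocol 6.1.9 defines baseline as the average of six predose readings on Day 1, and under Protocol 6.1.14 alarms use the lower threshold and events are timed. The supportive row is less certain. Below a baseline of 40 mmHg the alarm sits at baseline plus 10, and nothing in the documents says that a later crossing of 50 mmHg is timed or that continuous traces are kept.
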